7.4 Concomitant medication

- Description of the concomitant medication: number of patients and percentage of some concomitant medication will be presented by dose and ATC levels.

The following variables will be analyzed per visit:

- Requirement of another specific treatment for COVID-19 (Yes; No).
- Support treatment requirement (Yes; No). For those patients who have received supportive treatment, the treatment and description in the database (discrete) and the treatment scheme taking into account the active principle of the medication (discrete) will be analyzed. The number and percentage of patients that require each of the schemes will be indicated and a detailed list of patients will be provided.
- Duration of corticosteroids treatment.
- Duration of antibiotic treatment

8 EFFICACY EVALUATION

The efficacy analysis will be performed on the efficacy population. Results will be presented separately for treatment arm and for the main endpoints, by age (<65 or ≥65 years old) and by FDA classification will be performed too.

8.1 Efficacy evaluation

The following tests will be performed to evaluate the efficacy of the treatment:

a) Viral load evolution:

For the analysis of the evolution of the viral load, the number and percentage of patients from who a sample has been collected will be indicated to determine the viral load at baseline and at visit 4, 7, 15 and 31 describing the results in those patients (number of RNA copies detected and log of the number of copies). The result will be given to three decimal places.

The graphs of the evolution of the viral load (mean and median) of the patients from the baseline to the last visit will be presented. These graphs will be shown by separate for each dose level, by FDA baseline classification and Oxygen support or not on day 1.

In addition, the following variables will be analyzed:

- The number and percentage of patients who viral load result is maintained, decreased or increased with respect to the previous visit on days 4, 7, 15 and 31 will be presented.
- Negative detection (global and by dose level):
- The number and percentage of patients with negative or undetectable viral load on days 4,7,15 and 31.
- The number and percentage of patients with negative or undetectable viral load on days 4,7,15 and 31 in the subgroups of low, medium and high initial viral load.
- Time to negative detection (viral load 0 or undetectable) in overall patients from date of PCR at baseline.
- Time to negative detection (viral load 0 or undetectable) based on baseline viral load (high (>7 copies/mL) / medium [4-7 copies/mL] / low (<4 copies/mL)) and other baseline characteristics (sex, age, race, ...) will be explored.
- Time to negative detection based on corticosteroid treatment (<10 days vs > 10 days)
- Viral load (high, medium, low) will be correlated with study outcome variables such as need for oxygen therapy, admission to ICU (Yes / No), NIMV, IMV, days of hospitalization, death (Yes / No).

- Determine the relationship between the number of days with symptoms and having a higher or lower viral load.
- Determine the relationship between viral load and the baseline situation of the patient, mild-moderate-severe, oxygen need / no need.
- The relationship between viral load and different inflammatory parameters (LDH, ferritin, C-reactive protein, D-dimer and lymphocytes) will be graphically analyzed.
- The mean change in viral load log₁₀ RNA copies/mL from baseline to day 4, 7, 31 will be analyzed in:
 - All patients
 - Moderate and Mild Patients following the FDA Classification
 - Moderate patients following the FDA Classification

b) COVID-19 evolution by PCR:

For the analysis of COVID-19 evolution by PCR, the number and percentage of patients who have taken the PCR test will be indicated at the baseline and at visit 4, 7, 15 and 31 describing the results (positive / negative) in those patients.

A list of PCR evolution of the patients from baseline to the last visit will be presented.

c) Time to negative detection of COVID-19 detection by PCR:

The time to negative detection of the detection of COVID-19 by PCR is defined as the time, in days, from the date of baseline PCR to the first PCR date with a negative result and does not have a positive result in the following PCR or having a negative result in the last PCR date (Day 31).

The following analyses will be presented.

The time to negative detection will be analyzed by the Kaplan-Meier method and the median and the 95% confidence interval will be provided.

- The number and percentage of patients with qualitative PCR at 4, 7, 15 and 31 days
- A descriptive table will be provided in which both variables are related to each of the variables indicated below:
 - Chronic lung disease (excluding asthma) (Yes; No).
 - Oxygen therapy on day 1 (Yes; No).
 - Plitidepsin dose
 - Days from symptoms until 1st dose of plitidepsin
 - Baseline severity of the disease
 - Age
 - Sex
 - Use of corticosteroids
 - Race
 - Use of other antivirals or other specific treatments for COVID 19

d) Deaths:

The number and percentage of patients who die within 7, 15 and 31 days after starting the treatment with plitidepsin will be described.

- From day 1 to day 7
- From day 8 to day 15
- From day 16 to day 31

In addition, cumulative table will be presented with the following groups:

- From day 1 to day 7
- From day 1 to day 15
- From day 1 to day 31

e) Oxygen therapy:

The number and percentage of patients requiring oxygen therapy on days 7, 15 y 31 after the start of plitidepsin treatment.

- From day 1 to day 7
- From day 8 to day 15
- From day 16 to day 31

In addition, cumulative table will be presented with the following groups:

- From day 1 to day 7
- From day 1 to day 15
- From day 1 to day 31

A descriptive table will be provided in which both variables are related to each of the variables indicated below at 4, 7, 15 and 31 days:

- Chronic lung disease (does not include asthma) (Yes; No).
- Oxygen therapy at baseline (Yes; No).
- Days from the onset of symptoms (continuous).
- Demographic characteristics (Age, Sex, Race)
- Baseline viral load (high, medium, low)
- FDA classification at baseline

A listing with the evolution of oxygen therapy in each of the controls performed on the patients, indicating the type of oxygen therapy (Room air; Oxygen therapy; Not available) and the flow will be provided.

Onset day of oxygen therapy from the onset day of symptoms, start of treatment with plitidepsin, start of treatment with corticosteroids reported in concomitant medication form.

f) Oxygen therapy (High flow):

High flow oxygen therapy is defined as the use of venturi mask or High Flow Nasal Cannula (HFNC) as oxygen therapy.

The number and percentage of patients requiring high flow oxygen therapy will be provided.

- From day 1 to day 7
- From day 8 to day 15
- From day 16 to day 31

In addition, cumulative table will be presented with the following groups:

- From day 1 to day 7
- From day 1 to day 15
- From day 1 to day 31

Percentage of patients who change from low flow to high flow oxygen therapy.

g) Oxygen therapy (Low flow):

Low flow oxygen therapy is defined as the use of all oxygen therapy techniques except the ones use in high flow oxygen therapy.

The number and percentage of patients requiring low flow oxygen therapy will be provided.

- From day 1 to day 7
- From day 8 to day 15
- From day 16 to day 31.

In addition, cumulative table will be presented with the following groups:

- From day 1 to day 7
- From day 1 to day 15
- From day 1 to day 31

Percentage of patients who change from high flow to low flow oxygen therapy.

h) Mechanical ventilation (Invasive):

The following analysis will be performed:

- Total patients requiring Invasive Mechanical ventilation (95% IC)
- Number and percentage of patients requiring invasive mechanical ventilation
 - From day 1 to day 7
 - From day 8 to day 15
 - From day 16 to day 31
- In addition, cumulative table will be presented with the following groups:
 - From day 1 to day 7
 - From day 1 to day 15
 - From day 1 to day 31
- A descriptive table in which this variable is related to each of the variables indicated below at 4, 7, 15 and 31 days from the start of treatment will be provided:

- Chronic lung disease (does not include asthma) (Yes; No).
 - Oxygen therapy at baseline (Yes; No).
 - Days from onset of symptoms (continuous).
- If the patient has required invasive mechanical ventilation, the following analyses will be presented:
 - Number and percentage of patients who previously required non-invasive mechanical ventilation during the study.
 - Number and percentage of patients who previously required oxygen therapy during the study.
 - Number and percentage of patients with non-invasive mechanical ventilation after invasive mechanical ventilation.
 - Number and percentage of patients with oxygentherapy low/high flow after invasive mechanical ventilation.
 - Onset day of IMV with respect to the days of onset of symptoms, start of treatment with plitidepsin, start of treatment with corticosteroids reported in concomitant medication form.
 - Use of other specific COVID 19 treatments.
 - Duration of invasive mechanical ventilation (continuous): The duration of invasive mechanical ventilation is defined as the time from the first day when invasive mechanical ventilation is used until invasive mechanical ventilation is removed.

i) Mechanical ventilation (Non-Invasive):

The following analysis will be performed:

- Total patients requiring Non-Invasive Mechanical ventilation (95% IC)
- Number and percentage of patients requiring non-invasive mechanical
 - From day 1 to day 7
 - From day 8 to day 15
 - From day 16 to day 31
- In addition, cumulative table will be presented with the following groups:
 - From day 1 to day 7
 - From day 1 to day 15
 - From day 1 to day 31
- Time of non-invasive mechanical ventilation (continuous): The duration of non-invasive mechanical ventilation is defined as the time from the first day when non-invasive mechanical ventilation is used until the non-invasive mechanical ventilation is removed.
- If the patient has required non-invasive mechanical ventilation, the following will be analyzed:
 - Number and percentage of patients who previously required invasive mechanical ventilation during the study.
 - Number and percentage of patients who previously required oxygen therapy during the study.

- Number and percentage of patients with invasive mechanical ventilation after non-invasive mechanical ventilation.
- Number and percentage of patients with oxygentherapy low/high flow after non-invasive mechanical ventilation.
- Onset day of NIMV from the onset day of symptoms, start of treatment with plitidepsin, start of treatment with corticosteroids.
- Use of other specific COVID 19 treatments

j) ICU admission:

The following variables will be analyzed:

- Total patients requiring ICU (95% IC)
- Number and percentage of patients requiring ICU admission since the start of treatment with plitidepsin.
 - From day 1 to day 7
 - From day 8 to day 15
 - From day 15 to day 31
- In addition, cumulative table will be presented with the following groups:
 - From day 1 to day 7
 - From day 1 to day 15
 - From day 1 to day 31
- A descriptive table in which this variable is related to each of the variables indicated below at 4,7, 15 and 31 days from the start of treatment will be provided:
 - Chronic lung disease (does not include asthma) (Yes; No).
 - Oxygen therapy at baseline (Yes; No).
 - Days from onset of symptoms (continuous)
- Time in ICU admission (continuous): The time in ICU is defined as the time, in days, from ICU admission to ICU discharge. It will be only calculated for those patients who have been admitted and discharged from the ICU.
- Onset day of ICU admission (continuous): Onset day of ICU admission is defined as the time, in days, from the date of the first dose of plitidepsin treatment to the date of admission to the ICU. It will only be calculated for those patients who have been admitted to the ICU.
- Use of corticosteroids and/or antiviral and other specific COVID 19 treatments
- Time from ICU admission to Hospital discharge (continuous): The time from ICU admission is defined as the time, in days, from the date of ICU admission to the date of discharge from the center. It will only be calculated for those patients who have been admitted and discharged from the ICU and have also been discharged from the center. Reason for ICU discharge (taken back to the ward; Death; Others).
- Invasive mechanical ventilation (Yes; No).
- Non-invasive mechanical ventilation (Yes; No).
- High flow oxygen therapy (Yes; No).

k) ICU admission or Mechanical ventilation (Invasive):

The following analysis will be performed:

- Number and percentage of patients requiring invasive mechanical ventilation or ICU admission since the start of treatment.
 - From day 1 to day 7
 - From day 8 to day 15
 - From day 16 to day 31
- In addition, cumulative table will be presented with the following groups:
 - From day 1 to day 7
 - From day 1 to day 15
 - From day 1 to day 31

l) Hospitalization:

The following variables will be analyzed:

- Hospital discharge (Yes / No). If not, a list of reasons will be provided.
- Time to Hospital discharge (continuous): The time to Hospital discharge is defined as the time, in days, from the date of treatment start and the date of hospital discharge. In those patients who have not been discharged, the time, in days, from the date of first dose to the last available date will be calculated and it will be censored for time to event analyses. The description of the variable will be done separately depending on whether the patient has been discharged from hospital or not. The median and 95% confidence interval will be presented.
- Time from admission to Hospital discharge (continuous): The time to Hospital discharge is defined as the time, in days, from the date of admission and the date of hospital discharge
- Multivariate analysis will be done to evaluate the relationship of the main covariates in the analysis with Hospital discharge on Day 8 (Yes/No) and Hospital discharge on Day15 (Yes/No) by means of logistic regression models. More relevant exploratory covariates from the univariate analyses (p-value < 0.10) will be included in the multivariate analyses.
- Multivariate analysis will be done to evaluate the relationship of the main covariates in the analysis with time to hospital discharge by means of Cox proportional hazard models. More relevant exploratory covariates from the univariate analyses (p-value < 0.10) will be included in the multivariate analyses.
- Swimmer plot Hospital Discharge Day by Viral Load at Baseline, Disease Severity at Baseline and oxygen (yes/no) at baseline.

m) Class at discharge:

The time to hospital discharge (category 1) at 6-points ordinal scale will be analyzed by the Kaplan-Meier method and the median and the 95% confidence interval will be provided.

The analysis will be completed by the following subgroups:

- FDA classification
- Oxygen therapy on day 1
- Symptoms evolution less or equal/greater than 6 days.

The value of the 6-point ordinal scale will be derived from CRF data by using the following definition:

1. Discharge (Alive)
2. Hospital admission, not requiring supplemental oxygen.
3. Hospital admission, requiring supplemental oxygen.
4. Hospital admission, requiring high-flow nasal cannula or non-invasive mechanical ventilation.
5. Hospital admission, requiring extracorporeal membrane oxygenation or invasive mechanical ventilation.
6. Death.

In addition, the following analyses will be performed:

- Distribution of patients on the 1st day of the administration of plitidepsin, and on days 7, 15 and 31 will be analyzed according to the 6-points ordinal scale value.
- Number and percentage of patients who improve at least one point on the scale on day 7, 15 and 31.
- Number and percentage of patients who improve at least two point on the scale on day 7, 15 and 31.
- Number and percentage of patients who improve at two point on the scale or are discharged (whichever comes first) on day 7, 15 and 31.

n) FDA risk groups

FDA risk groups will be derived from CRF data according to the following definition:

- Mild: if positive testing by standard RT-PCR assay or equivalent test, symptoms of mild illness with COVID-19 that could include fever, cough, sore throat, malaise, headache, muscle pain, gastrointestinal symptoms, without shortness of breath or dyspnoea, no clinical signs indicative of moderate, severe, or critical severity.
- Moderate: if positive testing by standard RT-PCR assay or equivalent test, symptoms of moderate illness with COVID-19, which could include any symptom of mild illness or shortness of breath with exertion, clinical signs suggestive of moderate illness with COVID-19 such as respiratory rate ≥ 20 breaths per minute but < 30 breaths per minute, SpO₂ $> 93\%$ but $< 95\%$ on room air at sea level, heart rate ≥ 90 beats per minute but < 125 beats per minute, no clinical signs indicative of severe or clinical illness severity.
- Severe: if positive testing by standard RT-PCR assay or equivalent test, symptoms of moderate illness with COVID-19, which could include any symptom of moderate illness or shortness of breath at rest, or respiratory distress. Clinical of severe systemic illness with respiratory rate ≥ 30 breaths per minute, SpO₂ $\leq 93\%$ on room air at sea level, heart rate ≥ 90 beats per minute but ≥ 125 beats per minute or PaO₂/FiO₂ < 300 , no criteria for critical severity. Severinghaus equation was use to calculate PaO₂/FiO₂ as follow: $paO_2 = (B+A)^{1/3} - (B-A)^{1/3}$, where $A = (11700) * (S - 1) - 1$; S= Oxygen saturation; $B = (503 + A2)^{1/2}$ then PaO₂/FiO₂ = PaO₂/FiO₂ *100. (See appendix VI)

The following analysis will be done according to FDA risk group (days of hospital admission, need for high-flow oxygen, NIMV, IMV, admission to the ICU).

Relationship between the baseline severity of the disease, the initial viral load and the time it takes to become negative.

Relationship between days of symptom evolution and disease severity.

Analysis of differences in inflammatory parameters (CRP, ferritin, transaminases, LDH) and hematological (lymphocytes) and level of viral load in patients according to the risk group of the FDA.

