- Rheumatic disorder (Yes/No).
- Moderate or severe liver disease (Yes / No).
- Mild liver disease (Yes/No).
- Dementia (Yes/No).
- Malnutrition (Yes/No).
- Chronic neurological disorder (Yes / No).
- Smoker (Yes/No).
- Malignant neoplasm (Yes/No).
- Chronic hematological disease (Yes / No).
- AIDS / HIV (Yes / No).
- Obesity (define by medical staff) (Yes/No).
- Other risk factors (Yes / No). If so, the description of the specified factors will be detailed.

e) Vital signs at baseline

- SBP (mmHg) (continuous).
- DBP (mmHg) (continuous).
- Heart rate (l.p.m.) (continuous).
- Respiratory rate (r.p.m.) (continuous).
- Temperature (°C) (continuous).
- Saturation O₂ (%) (continuous).
- Saturation (Room air/Oxygen therapy/Not available). In the case of oxygen therapy, the following will be described:
 - Oxygen therapy type (Nasal glasses; Simple mask; Venturi mask; Reservoir mask; Other). In case of other a detailed listing will be provided.
 - Flow (L/min) (continuous).
 - FiO₂ (%) (continuous).
 - PaO₂ (mmHg) (continuous)
 - PaO₂/FiO₂ o SaO₂/FiO₂ (continuous).
- Chest X-ray (Yes/No). if so, the following will be described:
 - X-ray result (Normal/Abnormal). In case of abnormality, the abnormality will be detailed (Unilateral Pneumonia / Bilateral Pneumonia / Other). In case of other abnormality, the description of the abnormalities will be provided.
- Electrocardiogram (Yes / No). If so, it will be described:
 - Result (Normal / Abnormal: Not clinically significant or Abnormal: clinically significant). In case of abnormality, the description of the abnormalities will be provided. (QT interval prolongation / PR interval prolongation / other alteration). In case of other alteration, the description of the other alteration will be provided.

f) Viral load (log copies / mL)

g) Summary of Demographic and Other Baseline Characteristics

- Age, median (range) years

- Gender, % male
- Median (range) time from symptom onset to first plitidepsin administration, days
- Number of comorbidities, n (%) (none, one, two or more)
- Comorbidities, n (%) (Cardiac disease, Kidney disease, Liver disease, Lung disease (COPD), Asthma, Diabetes, Hypertension, Obesity)
- Clinical status at randomization, n (%)
- Vital signs, median (range) (Body temperature, °C, Systolic blood pressure, mmHg, Diastolic blood pressure, mmHg, Heart rate, bpm, Respiratory rate, bpm, SpO2 B, %, On oxygen at baseline, n (%))

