- Laboratory parameters, median (range) (WBC, x109/L, Platelet count, x109/L, Lymphocytes, x109/L, Serum creatinine, µmol/L, ALT x ULN, AST x ULN, LDH x ULN, CPK x ULN, GGT x ULN, C-reactive protein, Ferritin, D-dimer)
- log10 copies/mL viral load, median (range)

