Table 10.2.6 Clinical data (Signs and symptoms on admission) Baseline Characteristics

n (%)	Dose Cohort			
	1.5 mg N=X	2.0 mg N=X	2.5 mg N=X	Total N=X
*				

(*) Time from the beginning of the first symptom to hospital admission, Time from hospital admission to first dose of plitidepsin treatment, Fever, Dehydration, Cough, Sputum production, Hemoptysis, Runny nose, Earache, Crackles, Thoracic Pain, Muscular pain, Joint pain, Fatigue, Short of breathe, Intercostal retraction, Headache, Confusion, Convulsion, Abdominal pain, Vomiting\Nausea, Diarrhea, Conjunctivitis, Rash, Skin ulcer, Lymphadenopathy, Throat pain, Bleeding.

Table 10.2.7 Clinical data (Comorbidities) Baseline Characteristics (categorical variables)

n (%)	Dose Cohort			
	1.5 mg N=X	2.0 mg N=X	2.5 mg N=X	Total N=X
*				

(*)Chronic Cardiac pathologies, Arterial Hypertension, Chronic lung disease, Asthma, Diabetes with complications, Diabetes without complications, Chronic kidney disease, Rheumatic disorder, Moderate or severe liver disease, Mild liver disease, Dementia, Malnutrition, Chronic neurological disorder, Smoker, Malignant neoplasm, Chronic hematological disease, AIDS, obesity, Other risk factors, Other details.

Table 10.2.8 Vital signs at baseline Characteristics (categorical variables)

n (%)	Dose Cohort			
	1.5 mg N=X	2.0 mg N=X	2.5 mg N=X	Total N=X
*				

(*) Saturation, Oxygen therapy type, Chest X-Ray, Electrocardiogram, Result, FDA classification

Table 10.2.9 Six-point ordinal scale on Day 1

n (%)	Dose Cohort			
	1.5 mg N=X	2.0 mg N=X	2.5 mg N=X	Total N=X
1 Discharge (Alive)				
2 Hospital admission, not requiring supplemental oxygen				
...				

Table 10.2.10 Days with symptoms according to baseline viral load

	Viral Load at baseline (copies/mL)			p-value(*)
	Low <4	Medium [4-7]	High >7	
Days with symptoms				

(*) Kruskal-Wallis

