APPENDIX III

12 EFFICACY EVALUATION

12.1 Efficacy evaluation

Table 12.1.1 Number of patients with PCR

Number of patients with PCR	Dose Cohort			
	1.5 mg N=X	2.0 mg N=X	2.5 mg N=X	Total N=X
Baseline				
Undetectable				
Positive				
Day ...				

Table 12.1.2 Viral load classification by dose level and total

Day	Viral Load at baseline (copies/mL)	Viral Load classification during treatment (copies/mL)			
		Low <4	Medium [4-7]	High >7	Total
Day 4	Low <4				
	Medium [4-7]				
	High >7				
	Total				
...(*)	Low <4				
	Medium [4-7]				
	High >7				
	Total				

(*) Days 7, 15 and 31

Listing 12.1.3 Viral load evolution

Subject id	Dose	Visit	Result	log10 viral load copies/mL

Table 12.1.4 Summary of Protocol-Specified Efficacy Endpoints. Cumulative results.

Endpoint from day 1 to	Dose Cohort			
	1.5 mg N=X	2.0 mg N=X	2.5 mg N=X	Total N=X
Patients discharged from hospital, n (%)				
Day 7				
Day 8				
Day 15				
Day 31				
Deaths at, n (%)				
Day 7				
Day 15				
Day 31				
Later than Day 31				
Patients requiring invasive mechanical ventilation and/or ICU admission at, n (%)				
Day 7				
Day 15				
Day 31				
Patients requiring invasive mechanical ventilation, n (%)				
Day 7				
Day 15				
Day 31				
Patients requiring ICU admission at, n (%)				
Day 7				
Day 15				
Day 31				
Patients requiring non-invasive mechanical ventilation at, n (%)				
Day 7				
Day 15				
Day 31				
Patients requiring oxygen therapy at, n (%)				
Day 7				
Day 15				
Day 31				
Patients requiring oxygen therapy (high flow) at, n (%)				
Day 7				
Day 15				
Day 31				
Patients requiring oxygen therapy (low flow) at, n (%)				
Day 7				
Day 15				
Day 31				

This table will be also performed by age (<65 vs. ≥65 year old (12.1.4.1)

This table will be also performed by FDA classification (12.1.4.2)

Table 12.1.5 Summary of Protocol-Specified Efficacy Endpoints. Non-cumulative results.

Endpoint	Dose Cohort			
	1.5 mg N=X	2.0 mg N=X	2.5 mg N=X	Total N=X
Patients discharged from hospital, n (%)				
Day 1 to Day 8				
Day 9 to Day 15				
Day 16 to Day 31				
Deaths at, n (%)				
Day 1 to Day 7				
Day 8 to Day 15				
Day 16 to Day 31				
Later than Day 31				
Patients requiring invasive mechanical ventilation and/or ICU admission at, n (%)				
Day 1 to Day 7				
Day 8 to Day 15				
Day 16 to Day 31				
Patients requiring invasive mechanical ventilation, n (%)				
Day 1 to Day 7				
Day 8 to Day 15				
Day 16 to Day 31				
Patients requiring ICU admission at, n (%)				

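### SAP 8.1 a) gives the viral-load strata (<4, 4-7, >7) in copies/mL rather than log10 copies/mL; programmed literally, nearly every detectable patient would be High

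*SAP*

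**What the plan says.** SAP 8.1 a) is the only place that defines the strata: "high (>7 copies/mL) / medium [4-7 copies/mL] / low (<4 copies/mL"). The same cut-offs return in two table shells with the same linear unit. Table 10.2.10 is headed "Viral Load at baseline (copies/mL"), and Table 12.1.2 uses that heading for its rows and "Viral Load classification during treatment (copies/mL") for its columns. Tables 12.1.8, 12.1.10, 12.1.11 and 12.1.13 print 4 and 7 without any unit.

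Elsewhere the scale is logarithmic. SAP 5.2 f) lists "Viral load (log copies / mL") and 5.2 g) lists "log10 copies/mL viral load, median (range"). Listing 12.1.3, directly after Table 12.1.2, has a column for "log10 viral load copies/mL". Tables 10.2.1 and 12.1.7 and the mean-change item in 8.1 a) also use log10.

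Both scales will be available to the programmer, because 8.1 a) asks for the "number of RNA copies detected and log of the number of copies". The protocol does not define the strata, and neither document gives a detection or quantification limit for the assay.

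**The concern.** A threshold is part of the analysis definition, and here its unit disagrees with the scale on which the variable is otherwise analysed. A programmer who meets 4 and 7 without a unit in the later tables has to go back to 8.1 a), which points to the raw-copies variable. Nothing in the SAP overrides that.

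The strata link viral load, a secondary endpoint, to days with symptoms, clearance, oxygen need, ICU admission, ventilation, hospital stay and death. Tables 10.2.10, 12.1.8 and 12.1.11 attach Kruskal-Wallis or Fisher p-values to comparisons across them. If almost all detectable patients share one stratum, those comparisons have little or nothing to compare. Even if the code is right, shells printed with the wrong unit would carry it into the report, and the strata could not be reproduced from the SAP.

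**Working it through.** No sample size, power or event count depends on these cut-offs, so there is no planned figure to reproduce. The check converts the cut-offs and asks how patients would be divided under each reading.

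**1. Conversion.** Read as printed: log10(4) = 0.602 and log10(7) = 0.845, so the Medium band is 0.845 − 0.602 = 0.243 log10 wide. Read as log10: 10^4 = 10,000 and 10^7 = 10,000,000 copies/mL. The two readings differ by 10^4/4 = 2,500 at the lower cut-off and 10^7/7 ≈ 1.43 million at the upper.

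**2. Share in each stratum.** The documents give no detection limit and no load distribution, so both are assumed. Baseline log10 load is taken as normal with mean μ from 3 to 7 and SD σ from 1 to 2, restricted to values above a detection limit L of 1, 5, 10 or 100 copies/mL. For L below 7 copies/mL, under the printed unit:

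P(High | detectable) = [1 − Φ((0.845 − μ)/σ)] / [1 − Φ((log10 L − μ)/σ)]

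The least favourable case is μ = 3, σ = 2, L = 1. The numerator is 1 − Φ(−1.078) = 0.859 and the denominator is 1 − Φ(−1.5) = 0.933, which gives 92.1%. When L exceeds 7 copies/mL, every detectable value is above the upper cut-off and the share is 100% whatever the distribution.

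| L (copies/mL) | μ, σ (log10) | Printed unit: Low / Medium / High (%) | log10: Low / Medium / High (%) |
|---|---|---|---|
| 1 | 3, 2 | 5.2 / 2.7 / 92.1 | 66.9 / 30.6 / 2.4 |
| 1 | 5, 1.5 | 0.1 / 0.1 / 99.8 | 25.2 / 65.7 / 9.1 |
| 5 | 3, 2 | 0.0 / 1.8 / 98.2 | 64.7 / 32.7 / 2.6 |
| 10 | 5, 1.5 | 0.0 / 0.0 / 100.0 | 25.0 / 65.9 / 9.2 |
| 10 | 6, 1.5 | 0.0 / 0.0 / 100.0 | 9.1 / 65.7 / 25.3 |

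Over the whole grid, the printed unit puts 92.1% to 100% in High for L = 1, 98.2% to 100% for L = 5, and 100% for L = 10 or 100. The log10 reading at L = 1 puts 0% to 50% in High.

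**3. Which scale was meant.** SAP 15.4 prints a logistic model for discharge at day 8 with a baseline viral-load estimate of 2.4408 and an odds ratio of 11.482; exp(2.4408) = 11.482 confirms that the ratio is per unit. If the unit were one copy/mL, a difference of 100 copies/mL would multiply the odds by exp(244.08), and 244.08/ln(10) = 106.0, so by about 10^106. That is not credible, so baseline load was evidently modelled on a log scale.

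**4. Undetectable values.** SAP 8.1 a) treats a load of zero or undetectable as negative: "Time to negative detection (viral load 0 or undetectable) in overall patients from date of PCR at baseline". Zero has no logarithm, SAP 4.6 foresees no imputation, and SAP 3 leaves missing values out of percentages. Once the strata are on the log10 scale, a patient who clears the virus could therefore drop out of the on-treatment columns of Table 12.1.2 unless a stratum is assigned.

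**The case against.** The strongest reply is that this is a label with log10 dropped. The SAP uses log10 in its baseline summaries, its listing and its change table, and some headings already separate log10 from the unit. The model in 15.4 points the same way. A competent programmer would see what was meant, and the affected analyses are exploratory in a descriptive study. Most of this stands: log10 was almost certainly intended, and the collapse occurs only if the rule is followed as written. What does not follow is that the wording is harmless. The linear unit appears in the definition and in two shells, nothing corrects it, and the raw variable it points to will exist.

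A reader might infer more than the documents support:

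- **That Low and Medium would hold no detectable patients.** This needs a detection limit above 7 copies/mL, which the documents do not give. With a lower limit a few percent could fall there.
- **That every table using the strata is wrong as printed.** Tables 12.1.8, 12.1.10, 12.1.11 and 12.1.13 carry no unit; they go wrong only by taking it from 8.1 a).
- **That all the swimmer plots are affected.** Only Figure 12.1.47 is by baseline viral load; Figure 12.1.48 is by severity and Figure 12.1.49 shows oxygen therapy.
- **That the strata were in fact coded on raw copies.** Nothing shows how they were coded. The log-scale term in 15.4 makes raw coding less likely without settling it, since that term appears to be continuous.

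The factors of 2,500 and 1.43 million describe the gap between the two scales. They do not measure an effect on any result.

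**Conclusion.** The strata are wrong as written in SAP 8.1 a) and in the shells of Tables 10.2.10 and 12.1.2. Applied literally, they would put about 92% to 100% of detectable patients in High under the assumed distributions with a limit of 1 copy/mL, and all of them if the limit is above 7 copies/mL. These shares rest on the assumed limit and on a log-normal load. The exploratory comparisons by stratum would then be uninformative: Tables 10.2.10 and 12.1.2 directly, and Tables 12.1.8, 12.1.10, 12.1.11 and 12.1.13 and Figure 12.1.47 through the 8.1 a) definition. In Table 12.1.2 little would remain beyond detectable against zero.

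The primary safety endpoints, the log10 change by dose in Table 12.1.7, time to negative detection overall and by dose, and the sample size do not depend on the strata. The correction should be made because it is an analysis threshold and costs almost nothing, but it does not threaten the trial's main conclusions.

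**What to change.** In SAP 8.1 a), write the strata as log10 copies/mL: low below 4, medium 4 to 7, high above 7 (that is, 10,000 and 10,000,000 copies/mL). Put the same unit in Tables 10.2.10, 12.1.2, 12.1.8, 12.1.10, 12.1.11 and 12.1.13, and in Figure 12.1.47 where it groups by the strata.

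As a minor addition, state whether an undetectable value (raw 0, no log) is classed as Low or shown as a separate category, both at baseline and on treatment.

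The cost is a text edit to the SAP and shells, with no new data and no redesign. If outputs already exist, confirm in the code which variable the strata were cut from. If it was log10, a clarifying note and corrected headers are enough; if it was raw copies, rerun the listed tables and the figure.
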